The proposed study is a rigorous test of clinical outcomes building on a training and supervision approach employed by [name] (consultant on this study)^{33,34}, [name]^{35,76}, and others³⁵ in RCTs in other LAMICs. This approach involves local, trained lay individuals (i.e., our feasibility study lay counselors) who act as the direct treatment model supervisors, under supervision themselves, by TF-CBT and mental health experts (i.e., [name] & [name]). Our team views this RCT as the first step in a broader research plan to test the effectiveness of TF-CBT in successive implementation stages that systematically increase local expertise and responsibility and decrease expert involvement, with the goal of enhancing our knowledge around effective, feasible, and sustainable implementation strategies in LAMICs. As stated in the recently released NIH/PEPFAR RFA, focused on HIV/AIDS specifically (i.e., RFA-AI-11-003): "scientific advances regarding the implementation of effective interventions have not kept pace."

3C2b. The comparison group for the RCT is a "usual care" (UC) condition (i.e., existing orphan support services; (see Section 3C3c for our preliminary studies on UC in TZ & KE; also see Human Subjects). We enroll 320 child-guardian dyads in each of the two conditions (TF-CBT & UC; 640 total), with half of the participants enrolled in TZ and half in KE (see Table 2). Both sites are mixed urban and rural areas, allowing testing of TF-CBT in both settings to examine any impact of setting variables (i.e. differences in UC; urban vs. rural) on clinical outcomes or implementation (e.g., fidelity, attendance). Equal numbers of males and females, and children in age groups 7-10 and 11-13 will be recruited for both TF-CBT and UC. In the POFO study we easily recruited nearly twice this number (e.g., 560) in each region, indicating that the population of OAC in the areas in which we plan to recruit are high enough to support the proposed sample.

Sample size estimates for the RCT were determined using effect sizes from TF-CBT RCTs conducted in the US^{81,104}, from outcomes obtained in our TZ feasibility trial, and data from the Zambia TF-CBT feasibility trial (see Section 3C5b; for Power Analyses). Each site has a local UC group to enhance internal validity, given unique cultural, historical, political, religious, and ethnic differences, including relatively recent election riots experienced in KE.

	Moshi, TZ		Bungoma, KE	
	Urban	Rural	Urban	Rural

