Preliminary Studies Examining Usual Care Services. We examined supports and services received by orphans in TZ and KE using our longitudinal data from POFO. At baseline, nearly half of all POFO study participants in the Bungoma, KE (49%) and Moshi, TZ (42%) regions received at least some support in the form of food, clothing, educational assistance, money, childcare, counseling/emotional support, medical care, and/or transportation. At 36-months, rates of support remained stable in TZ (48%) and increased dramatically in KE (91%), mostly due to the influx of services following political violence (although anecdotal evidence indicates that this high level of support is has not been maintained). Support services were received from community, religious, and government organizations, as well as from friends and family. At the 36-month POFO follow-up, 31% of the KE respondents and 15% of the TZ respondents reported that they were receiving counseling/emotional support. The POFO children in KE also had higher rates of emotional and behavioral needs following the political violence than did those in TZ. Preliminary results from POFO indicate that recipients of support were those with higher emotional and behavioral needs (identified via Strengths and Difficulties Questionnaire, also used in the proposed study, see Table 4) and in worse physical health, suggesting that children with greater needs receive more services. The effectiveness of UC services in improving outcomes is unknown. ACE Africa and TAWREF are aware of the local support services to which participants can and will be referred (in addition to those provided by their own organization), and each have established a local Standard of Care document (see Appendix C for Bungoma, KE example).

3C4. Assessment and Data Collection Procedures

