For example, where the outcome is the level of symptoms for a given client i in group g ; B_{0g} (the intercept) represents the average 12-weeks level of symptoms for all children in a given group g , B_{1g} is the effect of pre-treatment symptoms, B_{2g} is the effect of

child/guardian-level covariates (such as demographics: child age, gender), and e_{it} represents residual variance in the outcome for individual i in group g . If randomization was effective, the effects of pre-treatment symptoms may be ignored. The Level 2 equations represent how the coefficients at Level 1 are distributed across treatment groups. Both the intercept and the effects of pre-treatment symptoms (if needed) would be specified as random variables, which would allow their effects to differ across treatment groups. The level 2 equation would follow the general form of $B_{0g} = \pi_{00} + \pi_{01}Treatment + r_{00}$, which uses condition-level variables (such as assignment to TF-CBT or UC) to predict how effects differ. Thus the hypothesis that group-based TF-CBT produces significant improvements in symptoms over the UC condition would be tested by evaluating the significance of π_{01} above, which tests the effects of condition assignment on 12-week symptoms.

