These aims would be tested by adding country and rural or urban setting as predictors at Level 2. These analyses would test whether country or setting explain between-condition differences in treatment outcomes at

a specific time point, and for the growth models, whether they explain differences between conditions in the rate of change over time.

Aim 3. Examine the impact of implementation factors (e.g., TF-CBT fidelity, lay counselor-supervisor relationship, child/guardian attendance) on outcomes.

Analyses for Aim 3 will focus on how implementation variables (such as attendance, fidelity, provider knowledge) are related to outcomes at 12-14 weeks (end of TF-CBT) and at the follow-ups. These analyses will be restricted to those in the TF-CBT condition. These Aims are tested by expanding the models described in Aims 1 and 2, above, to include implementation variables at both the individual level (such as attendance) and the group level (TF-CBT fidelity). For example, MLM equations that look at implementation effects on post-treatment levels of symptoms could be:

Level 1:	$Symptoms_{ig} = B_{0g} + B_{1g}PreSx + B_{2g}Cov + B_{3g}Attendance + e_{ig}$
Level 2:	$B_{0g} = \pi_{00} + \pi_{01}Fidelity + r_0$ $B_{1g} = \pi_{30}$ $B_{2g} = \pi_{30}$ $B_{3g} = \pi_{30} + r_2$

These models test how attendance during treatment and fidelity of the treatment provider influence symptoms at 12-weeks and at follow-ups, treating the intercept and the effects of attendance as random effects, and the

effects of pre-treatment symptoms and covariates as fixed effects.

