3C5c Power. Power analyses were conducted using Optimal Design 2.0¹²⁴. A primary concern when estimating power in HLM focuses on the Interclass Correlation Coefficient (ICC) for providers, as providers are nested within conditions. Higher positive ICCs result in less statistical power, and few estimates of provider ICCs for fidelity to treatment are available. A review of 20 studies predicting client functioning found provider ICCs clustering from -0.1 to .06¹²⁵. Because precise estimates for ICCs are unknown, we examined ICC thresholds within a range of effect sizes (with .05 Type I error rate, power of .80, 8 children per TF-CBT group; 320 children total). Estimates did not include the effect of covariates which, if moderately correlated with the outcome variable, will increase statistical power. Therefore, these estimates present a conservative estimate. Our primary hypothesis test (i.e. differences at 12-weeks between TF-CBT & UC) is sufficiently powered ($1-\beta = .80$) to detect small effects (.35) with ICCs up to .15, moderate effects (.50) with ICCs up to .30, and all conceivable large effects. For detecting condition differences in terms of the linear or quadratic slope, analyses suggested that the proposed *N* has power ($1-\beta = .80$) to detect effects as small as .29 on slopes. Finally, for Aim 3, the current sample of 320 individuals in the TF-CBT condition, the current study is sufficiently powered to detect small (.21) effects of individual implementation variables on outcomes, but with only 20 clusters (i.e., groups) the study will have less power to detect all but large effects of group-level variables (e.g., fidelity).

3C6. Rationale of Choices Made in the Research Design. Our team carefully considered various design and methodological challenges, our rationale for various decisions is discussed here.

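### The primary Aim 1 model omits country and setting, although enrolment is planned to be equal across them, so the treatment standard error may be larger than it need be

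*Combined protocol and SAP*

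**What the plan says.** **Model.** Section 3C5b writes the 12-week Aim 1 test as a two-level model, with clustering in the TF-CBT arm only. Level 1 holds pre-treatment symptoms and a covariate term, described as "child/guardian-level covariates (such as demographics: child age, gender". At Level 2, Treatment is the only predictor of the intercept. The text allows pre-treatment symptoms to be dropped if randomisation worked. Country and setting first appear under Aim 2: "These aims would be tested by adding country and rural or urban setting as predictors at Level 2".

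**Design.** Section 3C2b says "We enroll 320 child-guardian dyads in each of the two conditions", "with half of the participants enrolled in TZ and half in KE". Table 2 gives 80 per arm in each country-by-setting cell. Section 3C3b plans 20 TF-CBT groups per region, 10 urban and 10 rural. That makes 40 groups of 8, each lying in one cell.

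**Other covariate provisions.** Section 3C5a allows unnamed covariates in a later robustness step. The opening of 3C5 allows control for minor baseline differences and lists symptoms, trauma history, gender and age. Neither names country or setting.

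**Evidence on the countries.** Section 3C3c reports from the earlier orphan cohort: "The POFO children in KE also had higher rates of emotional and behavioral needs following the political violence than did those in TZ".

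**Power.** Section 3C5c claims .80 power "to detect small effects (.35) with ICCs up to .15, moderate effects (.50) with ICCs up to .30". It adds: "Estimates did not include the effect of covariates which, if moderately correlated with the outcome variable, will increase statistical power".

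**The concern.** Equal planned numbers per arm in every cell mean that country and setting cannot shift the arm comparison. A model without those factors does not know this. In the TF-CBT arm, differences between cells look like differences between groups. The group variance is divided by only 40 groups, so it weighs heavily in the treatment standard error. In usual care, which has no groups, the same differences go into the residual.

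The design would then have removed a source of noise that the analysis puts back. What is at stake is precision: a wider interval and some lost power on the main comparison. It also matters that the primary model is fixed in advance, because the choice to add these factors is otherwise left to an unspecified later step.

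**Working it through.** **1. The plan's own power figure.** Section 3C5c gives its inputs as "with .05 Type I error rate, power of .80, 8 children per TF-CBT group; 320 children total". Sidedness is not stated; I assume two-sided. The target is .80 at (effect .35, ICC .15) and at (.50, .30).

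- Cluster-randomised formula, SE = √(4(ICC + (1 − ICC)/8)/J): power .31 and .40 with J = 20; .57 and .70 with J = 40; .86 and .94 with J = 80.
- Partially nested formula, SE = √((2 + 7·ICC)/n): .67 and .84 with n = 160 per arm; .94 and .99 with n = 320 per arm.

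No single variant gives .80 at both points. With all 640 children both exceed .80, so the claim then holds as a lower bound. I use the partially nested form with 320 per arm, which matches the design.

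**2. Standard error with the cells in the model.** Set the within-cell variance to 1. Then SE² = (2 + 7·ICC)/320.

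- ICC .05: 2.35/320 = .00734, SE = .0857.
- ICC .15: 3.05/320 = .00953, SE = .0976.

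**3. Standard error without the cells.** Let v be the share of total outcome variance lying between cells, and s = v/(1 − v). With balanced cells, the sample variance of the 40 group means rises by 40s/39, which adds s/39 after division by 40. The usual-care variance rises by 320s/319, which adds s/319. So SE² = (2 + 7·ICC)/320 + s/39 + s/319.

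Example at ICC .15, v = 5%: s = .0526, and .00953 + .00135 + .00016 = .01105, so SE = .1051. The group-level route carries (1/39)/(1/39 + 1/319) = 89% of the excess and the usual-care residual 11%. The apparent ICC becomes (.15 + .0526)/1.0526 = .193.

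**4. Power at the plan's .35.** With balanced cells the estimate's true sampling error is the SE from step 2, but the test uses the SE from step 3. Without the cells, power is Φ((.35 − 2.023 × SE without)/SE with), where 2.023 is the 97.5% point of t on 39 df. With the cells, a noncentral t is used.

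The documents give no value for v, so the shares below are assumptions. Pre-treatment symptoms are not adjusted for.

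| ICC | v | SE with | SE without | Increase | Power with | Power without |
|---|---|---|---|---|---|---|
| .05 | 1% | .0857 | .0874 | 2.0% | .978 | .978 |
| .05 | 2% | .0857 | .0891 | 3.9% | .978 | .976 |
| .05 | 5% | .0857 | .0941 | 9.8% | .978 | .969 |
| .05 | 10% | .0857 | .1027 | 19.8% | .978 | .952 |
| .15 | 1% | .0976 | .0991 | 1.5% | .938 | .937 |
| .15 | 2% | .0976 | .1006 | 3.0% | .938 | .933 |
| .15 | 5% | .0976 | .1051 | 7.7% | .938 | .920 |
| .15 | 10% | .0976 | .1128 | 15.6% | .938 | .894 |

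At v = 0 the increase is nil.

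**5. Simulation check (4,000 trials per setting, ICC .15).** At v = 5%, the mean model SE was .1049 without cells and .0974 with; type I error was .035 and .048. At v = 10%, the SEs were .1125 and .0974, and type I error .022 and .051. A small set of mixed-model fits (40 per setting, some with convergence warnings) gave SE ratios of 1.00, 1.08 and 1.16 at v = 0, 5% and 10%. Dropout was not modelled.

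**The case against.** **The size is assumed.** This stands. No section reports a between-cell variance. The cohort statement on higher Kenyan needs is tied to the political violence. The 31% against 15% receiving counselling come from that cohort's 36-month follow-up, and 3C3c says, on anecdotal evidence, that the high Kenyan support has not lasted. Baseline shares with any support were close (49% and 42%). Service use is not outcome variance, no urban-rural symptom difference is reported, and the trial's symptom threshold at entry may narrow country differences. A reader might infer that the documents establish a known loss; they make some difference plausible and no more.

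**Pre-treatment symptoms are in the printed equation.** If kept, they absorb part of any cell difference, so the table is an upper reading for a given share. The plan also permits dropping them.

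**The plan already has room for these factors.** The covariate list is illustrative, a robustness step exists, and Aim 2 fits models containing country and setting. But the covariate slot is for child or guardian variables, the plan itself places country and setting at Level 2, and the robustness step names nothing. What remains open is which model is primary.

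**Balance rests on planned counts.** Section 3C4d does not say that randomisation is stratified by cell, and it refers to a Human Subjects section that is not among the documents. If counts come out uneven, adjustment also corrects the chance imbalance.

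**Stronger readings that fail.** A reader might infer bias or a false-positive risk. With balanced cells there is no bias, and type I error falls below .05. A reader might also infer that the trial is underpowered. At an effect of .25, ICC .05 and v = 10%, approximate power is Φ((.25 − 2.023 × .1027)/.0857) = .69 without the cells and Φ(.25/.0857 − 2.023) = .81 with them. But .25 is not a 12-week effect in 3C5c, and 10% is the top of an assumed range.

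**Conclusion.** The omission is clear from the text, and its direction is certain if cells differ: the treatment standard error is larger than necessary and the test is conservative. Most of the excess, about 89%, comes through the TF-CBT group variance and the rest through the usual-care residual, so it is not all counted as clustering.

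The size is not known. Over an assumed between-cell share of 0 to 10%, with ICC .05 to .15, planned cell counts met and no pre-treatment adjustment, the standard error is about 0 to 20% too large. At the plan's .35 with 640 children, the power loss is at most about 4 points (.938 to .894). This is avoidable imprecision that does not make the analysis invalid: a free improvement.

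**What to change.** In 3C5b, name country, setting and their interaction (the four Table 2 cells) as fixed effects in the primary Aim 1 model at 12 weeks. In the growth models, include the same terms together with their time terms. Keep treatment-by-country and treatment-by-setting terms for Aim 2.

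The cost is a line of text and three degrees of freedom in the 12-week model, plus three for each time term in the growth models. No new data are needed, because Aim 2 already requires both variables.

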[^] C= Child, G=Guardian, LC=Lay Counselor; RC: Research Coder (i.e., Data entry person) [*] BL = Baseline; 12w = 12-14 weeks; 6M = 6 months; 12M = 12 months [#] Post-T = Post-Training; Post C1: after delivery of one 1 cycle of groups (2 groups); Post C2: after delivery of 2 nd cycle of groups [†] Measure used in the TF-CBT for CTG Feasibility Study ⁺ Measures used in POFO (both TZ and KE)			

3C5. Data Analysis Plan

Basic data screening procedures will be conducted (e.g., means, standard deviations, skewness, plotting relationships) to screen for errors and explore normality, linearity, form, and outliers. Data will be transformed as appropriate. We will confirm the assumption of randomization at baseline by testing cohort differences in outcome variables (i.e. symptoms), history of traumatic events and basic demographics (i.e. gender and age). Minor differences will be controlled for in statistical models as described below. Statistical analyses for the main aims will be conducted using the SPSS¹¹⁸, Stata¹¹⁹ and Multilevel/Hierarchical Level Modeling¹²⁰ (MLM/HLM) software programs. HLM allows for the presence of missing data at Level 1 (such as when participants are lost to follow-up) appropriately adjusting for data missing at random, particularly when covariates associated with missingness are included in the statistical model¹²¹.

3C5a. Overview of Modeling Approach. Hypotheses related to Aim 1 will be tested using MLM (i.e. HLM, random coefficient models, mixed effects models), which are a powerful and flexible class of analytic approaches that allow for the analysis of non-independent data. MLM allow researchers to account for nesting within different data structures and to explicitly model effects across nested groups. For the current study, the outcome data will be observations of clinical outcomes at multiple time points, nested within children, who are also nested within TF-CBT groups (for the TF-CBT condition). Not accounting for the fact that some children are treated in the same treatment group, for example, could lead to biased estimates. The MLM approach reduces Type I errors caused by violating assumptions of independence, allows time-varying assessments and increases power by utilizing information from multiple time points in a single model.

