We will test hypotheses through a standard approach to model-building, focusing on creating parsimonious explanatory models through progressive taxonomies as follows^{122,123}. An unconditional model (i.e. one without predictors) of the outcome will be fitted first, which allows specification of the random effects, which in turn provides an estimation of the amount of interdependence at each level of clustering. For longitudinal models including multiple time points (i.e. client outcomes from baseline to follow up assessments), an unconditional growth model will be fit to identify time trends and inter-individual variance in trends. We will next test the effects of the primary variable of interest (e.g., condition assignment, or therapist fidelity to treatment model) on the outcome in a conditional model (i.e., one with predictors). Finally, theoretically relevant covariates will be

added to determine the robustness of the main effects. Relative goodness-of-fit for each successive model will be evaluated using likelihood ratio tests and deviance statistics.

3C5b. Primary Analyses

Aim 1. Test the effectiveness of a group model of TF-CBT for orphaned youth in two East African countries, including any variation by child age and gender.

Hypothesis 1: Children in the TF-CBT condition will demonstrate greater reductions in symptoms and greater improvement in overall functioning and the child-guardian relationship.

These analyses focus on whether TF-CBT produces significant reductions in symptoms (i.e. CTG, PTS, depression, behavioral problems) or improvement in functioning, or the child-guardian relationship compared to UC. Hypotheses will be tested in two ways using MLM. First, we test whether the TF-CBT condition differs from the UC condition at 12-weeks (i.e., end of TF-CBT). This hypothesis will be tested with a simple 2-level MLM, predicting the observed outcome (by child or guardian report) at 12-weeks, while accounting for clustering of individuals within TF-CBT groups, for the TF-CBT condition. The general Level 1 equation, which models individual differences in symptoms at 12-weeks, would be as follows:

Level 1:	$Symptoms_{ig} = B_{0g} + B_{1g}PreSx + B_{2g}Cov + e_{ig}$
Level 2:	$B_{0g} = \pi_{00} + \pi_{01}Treatment + r_{00}$ $B_{1g} = \pi_{10} + r_{00}$ $B_{2g} = \pi_{20}$

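### The 12-week primary model allows the pre-treatment score to be dropped when randomization looks effective, with no criterion, which gives up precision and leaves the primary test undefined

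*Combined protocol and SAP*

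**What the plan says.** The Level 1 equation for the 12-week outcome in Section 3C5b (Aim 1) contains a pre-treatment symptom term, PreSx. The text after it makes that term optional: "If randomization was effective, the effects of pre-treatment symptoms may be ignored". The description of the random effects repeats the option: "Both the intercept and the effects of pre-treatment symptoms (if needed) would be specified as random variables".

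The check on randomization is in the opening paragraph of Section 3C5: "We will confirm the assumption of randomization at baseline by testing cohort differences in outcome variables". It is followed by "Minor differences will be controlled for in statistical models as described below". No significance level or size of difference is attached to either statement.

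Section 3C5a sets the order of model-building. After the unconditional models, "We will next test the effects of the primary variable of interest"; covariates come last and are "added to determine the robustness of the main effects". Successive models are compared by fit statistics.

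Two other places treat the baseline score differently. The Aim 3 model keeps it without any condition, treating the "effects of pre-treatment symptoms and covariates as fixed effects". Section 3C5c leaves covariates out of the power calculation but notes that covariates, "if moderately correlated with the outcome variable, will increase statistical power".

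**The concern.** Randomization makes the unadjusted comparison unbiased on average. It does not make a prognostic baseline score uninformative. Adjusting for that score removes outcome variance whether or not the arms look balanced, so a plan that drops it because the arms look balanced discards precision for nothing. Section 3C5c recognizes that correlated covariates add power.

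The second problem is pre-specification. The terms effective, minor and needed are undefined. The instruction to control for minor differences also pulls against permission to ignore the score. Section 3C5a adds a separate ambiguity: the condition effect is estimated before and after covariates enter, and the plan does not say which estimate is the primary test. The choice could be made after seeing the data, and made differently for each of the six outcome domains in Hypothesis 1 (traumatic grief, posttraumatic stress, depression, behavioral problems, functioning, child-guardian relationship).

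At stake are wider confidence intervals than necessary, chance baseline differences left in the estimate, and a primary result open to challenge.

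**Working it through.** **Inputs from the plan.** 320 children per arm (3C2b); TF-CBT groups of 8, with clustering in that arm only (3C5b); type I error .05 (3C5c), taken as two-sided. Two ICCs from 3C5c: .06, the top of the range in the cited review, and .15, the limit stated for an effect of .35.

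**Assumed input.** The correlation r between baseline and 12 weeks is not given; I use .3 to .6. The pilot table in 3C1d bounds it for one outcome. SDQ fell from 13.59 (SD 6.64) to 8.75 (SD 6.28), n = 32, p < .001. For a two-sided paired t-test the critical t(31) is 3.633, so the SD of change is at most 4.84 × √32 / 3.633 = 7.54. Hence r ≥ (6.64² + 6.28² − 7.54²) / (2 × 6.64 × 6.28) = .32. An unpaired test would give p = .004, so the paired reading is plausible. The same bound is uninformative for traumatic grief and depression.

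**The plan's own power figure.** With outcome SD 1 and no covariates, the variance of the treatment difference is V = (1 + 7 × ICC)/320 + 1/320. At ICC .15, V = 3.05/320 = .00953 and SE = .0976. Power for .35 is Φ(.35/.0976 − 1.96) = .95. The stated .80 is not reproduced exactly, but at N = 640 it holds as a floor. With the 320 children in total named in 3C5c, the same formula gives .72; that mismatch with the 640 in 3C2b is a separate matter.

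**With the baseline score.** If baseline explains r² of the individual-level variance and none of the between-group variance (a conservative choice), VA = V − 2r²/320. SE inflation from omission is √(V/VA) − 1, and the equivalent unadjusted sample is 640 × V/VA.

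| ICC | r | 320 × V | 320 × VA | SE inflation | 640 adjusted worth, unadjusted |
|---|---|---|---|---|---|
| .06 | .3 | 2.42 | 2.24 | 4% | 691 |
| .06 | .6 | 2.42 | 1.70 | 19% | 911 |
| .15 | .3 | 3.05 | 2.87 | 3% | 680 |
| .15 | .6 | 3.05 | 2.33 | 14% | 838 |

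At r = .5, with the detectable effect at 80% power equal to (1.960 + .8416) × SE:

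| ICC | Detectable effect, unadjusted vs adjusted | Power for .35 | Power for .25 |
|---|---|---|---|
| .06 | .244 vs .217 | .98 vs .995 | .82 vs .90 |
| .15 | .274 vs .250 | .95 vs .975 | .73 vs .80 |

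**Chance imbalance left in the estimate.** Its SD is r × √(2/320) = .024 to .047 outcome SDs over all randomizations. Restricted to trials whose baseline test is not significant at .05, it is .021 to .041. It averages to zero, so it is not bias of the estimator.

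**Type I error.** Under the null, the unadjusted and adjusted z-statistics are correlated √(VA/V).
- If whichever model is significant is reported, P(either |z| > 1.96) is .063 to .076 at ICC .06 and .061 to .073 at ICC .15.
- If a strict rule is followed (adjust only when the baseline difference has p < .05), 2,000,000 simulated trials per setting give .042 to .049, so there is no inflation.

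**How often the choice matters.** At a true effect of .25 and r = .5, the two models disagree on significance in 10% (ICC .06) to 12% (ICC .15) of trials.

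**The case against.** The strongest reply is that the plan ties the decision to baseline balance, which carries no information about the treatment effect, and that a balance-based rule does not inflate type I error. That is correct, so .061 to .076 is a worst case that requires choosing the model by its result. The plan does not propose this. It does not rule it out either, because there is no threshold and no named primary model.

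It can also be said that the displayed equation contains the score, that the wording only permits dropping it, and that minor differences are to be controlled for. Read that way, the score goes only when the arms look well balanced, and the residual imbalance is smaller: SD .013 to .026 if the baseline z-statistic is below 1 in size. This reduces the imbalance argument but not the precision argument, which applies fully in balanced arms.

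Third, little is lost at the planned effect. Power for .35 is high either way, and the stated power takes no credit for covariates. This stands, and it limits the severity.

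Fourth, r is assumed. The only pilot bound covers one outcome in 32 treated children interviewed by their own counselors, and selecting children on grief and stress scores could lower r for those outcomes. At r = .3 the cost is only 3% to 4% of the standard error. This also stands, and is why a range is given.

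Finally, the growth model uses the baseline data, so Aim 1 as a whole does not ignore them. But the 12-week comparison is the one Section 3C5c calls the primary hypothesis test, and Aim 2 builds on the same model.

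**Conclusion.** The concern holds. The plan permits a less precise primary test on a mistaken rationale, gives no rule for when the permission applies, and does not identify the model that supplies the primary treatment effect. No other section withdraws the option.

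The cost is moderate: a standard error 3% to 19% larger than necessary over the ranges considered, plus avoidable freedom in the choice of primary model. The unadjusted estimator is not biased and the trial is not underpowered for .35 at N = 640. The figures assume r between .3 and .6, a two-sided test, no dropout, clustering in the TF-CBT arm only, and baseline explaining individual-level variance only. If baseline also explained between-group variance, the gain from adjusting would be larger. The plan should be changed, but the point does not threaten the trial's validity.

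**What to change.** In Section 3C5b, delete the sentence "If randomization was effective, the effects of pre-treatment symptoms may be ignored" and the qualifier *if needed* in the description of the random effects. In Section 3C5, stop using baseline tests to decide on adjustment; baseline characteristics can be described by arm. State that, for every outcome and whatever the observed balance, the primary 12-week test of condition comes from the model that includes the baseline value of that same outcome. Any model without it, including the condition-only step in Section 3C5a, becomes a sensitivity analysis.

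Whether the PreSx slope is fixed or random, and which other covariates enter, are separate choices that this change does not touch.

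The change is to analysis-plan wording only. Table 4 already schedules every clinical outcome at baseline and 12 weeks, so no visit, measure or sample size is affected.
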